2.1.2 Secondary Efficacy Objective

The secondary efficacy objective for this study is to evaluate the efficacy of atezolizumab plus tiragolumab and atezolizumab plus placebo on the basis of the following endpoints:

- DOR for patients with confirmed objective response, defined as the time from the first occurrence of a documented confirmed objective response to disease progression, as determined by the investigator according to RECIST v1.1, or death from any cause, whichever occurs first
- PFS, defined as the time from randomization to the first occurrence of disease progression, as determined by the investigator according to RECIST v1.1, or death from any cause, whichever occurs first
- OS, defined as the time from randomization to death from any cause
- PFS rate at 6 months
- OS rate at 6 months and 12 months
- Time to confirmed deterioration (TTCD) in patient-reported physical functioning, as measured by the Patient-Reported Outcomes Measurement Information System® (PROMIS®) Item Bank v2.0–Physical Functioning–Short Form 10b

[REDACTED]

[REDACTED]

- [REDACTED]

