- **Arm A:** Patients will receive atezolizumab at a fixed dose of 1200 mg administered by IV infusion Q3W on Day 1 of each 21-day cycle, followed by tiragolumab at a fixed dose of 600 mg administered to patients by IV infusion Q3W on Day 1 of each 21-day cycle.
- **Arm B:** Patients will receive atezolizumab at a fixed dose of 1200 mg administered by IV infusion Q3W on Day 1 of each 21-day cycle, followed by placebo administered by IV infusion Q3W on Day 1 of each 21-day cycle.

Treatment may be continued as long as patients are experiencing clinical benefit, as assessed by the investigator, in the absence of unacceptable toxicity or symptomatic deterioration attributed to disease progression after an integrated assessment or radiographic data, biopsy results (if available), and clinical status. Patients who meet the criteria for disease progression per RECIST v1.1, but continue to have clinical benefit, will be permitted to continue treatment (atezolizumab plus tiragolumab or atezolizumab plus placebo) if they meet all of the criteria specified in Section 3.1.1 and provide written consent.

Patients will undergo tumor assessments at baseline, every 6 weeks (± 7 days) for the first 30 weeks following Day 1 of Cycle 1, and every 9 weeks (± 7 days) after completion of the Week 30 tumor assessment. Tumor assessments will continue per schedule regardless of treatment delays until radiographic disease progression per RECIST v1.1 or loss of clinical benefit for patients who continue study treatment after radiographic disease progression per RECIST v1.1, withdrawal of consent, death, or study termination by the Sponsor, whichever occurs first. At the investigator's discretion, scans must be performed at any time if progressive disease or loss of clinical benefit is suspected. Radiographic images will be submitted to an independent review facility.

(IRF) for a quality and completeness check, for potential blinded independent central review (BICR), and for temporary storage prior to transferring images to the Sponsor for the long-term retention and eventual secondary or exploratory use.

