6.1 DETERMINATION OF SAMPLE SIZE

A total of 120 patients will be enrolled in this study and randomized in a 2:1 ratio (atezolizumab plus tiragolumab and atezolizumab plus placebo). [REDACTED]

[REDACTED]

[REDACTED]

[REDACTED]

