6.4.2 Secondary Efficacy Endpoints

6.4.2.1 Duration of Response

DOR will be assessed in patients who have achieved a confirmed objective response, as determined by the investigator according to RECIST v1.1. DOR is defined as the time interval from the date of the first occurrence of a confirmed objective response until the first date of progressive disease, as determined by the investigator according to RECIST v1.1, or death from any cause, whichever occurs first. Patients who have not progressed and who have not died at the time of analysis will be censored at the time of the last tumor assessment date. Kaplan-Meier methodology will be used to estimate the median DOR for each treatment arm, and Kaplan-Meier curves will be produced. The Brookmeyer-Crowley methodology will be used to construct the 95% CI for the median DOR for each treatment arm (Brookmeyer and Crowley 1982).

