6.4.2.2 Progression-Free Survival, Including Progression-Free Survival Rate at 6 Months

PFS is defined as the time between the date of randomization and the date of first documented disease progression, as assessed by investigators according to RECIST v1.1, or death, whichever occurs first. Patients who have not experienced disease progression or have not died by the data cutoff date will be censored at the time of the last tumor assessment. Patients with no post-baseline tumor assessment will be censored at the date of randomization.

Kaplan-Meier methodology will be used to estimate the median PFS for each treatment arm, and Kaplan-Meier curves will be produced. The Brookmeyer-Crowley methodology will be used to construct the 95% CI for the median PFS for each treatment arm (Brookmeyer and Crowley 1982). The PFS rates at 6 months after randomization will be estimated using Kaplan-Meier methodology for each treatment arm, along with 95% CIs calculated using the standard error derived from Greenwood's formula.

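### Section 6.4.2.2 censors at randomization every patient without a post-baseline scan, with no exception for those who died, although death is a PFS event

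*Combined protocol and SAP*

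**What the plan says.** **Definition.** Section 2.1.2 lists "PFS, defined as the time from randomization to the first occurrence of disease progression" by investigator assessment, or death from any cause if that comes first. Section 6.4.2.2 repeats this with "or death, whichever occurs first".

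**Censoring.** Two sentences follow in Section 6.4.2.2. The first reads "Patients who have not experienced disease progression or have not died by the data cutoff date will be censored", with the last tumor assessment as the censoring date. The second reads "Patients with no post-baseline tumor assessment will be censored at the date of randomization". Neither says what happens to a patient who died without a scan.

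**Parallel rule.** For duration of response, Section 6.4.2.1 has "Patients who have not progressed and who have not died at the time of analysis will be censored", joining the two conditions with 'and'.

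**Estimator and schedule.** "The PFS rates at 6 months after randomization will be estimated using Kaplan-Meier methodology for each treatment arm". Section 3.1 sets the scan timing: "Patients will undergo tumor assessments at baseline, every 6 weeks" for the first 30 weeks, with a window of 7 days either way. Section 6.1 states "A total of 120 patients will be enrolled in this study and randomized in a 2:1 ratio", which is 80 and 40 patients.

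**The concern.** A patient who dies in, say, week 3 without a scan is a PFS event under the definition and a day-0 censored observation under the second censoring sentence. Both cannot apply, and nothing in the visible text says which prevails. A programmer would have to choose.

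The neighbouring endpoints handle the same patient clearly. Section 6.4.1 counts patients without a post-baseline assessment as non-responders. Section 6.4.2.3 limits the main OS censoring rule to patients not reported dead, and its own day-0 rule applies only where there is no post-baseline information at all. A death is itself such information, but it is not a tumor assessment, so the same pattern of wording is harmless for OS and not for PFS.

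At stake are the median PFS and the 6-month PFS rate in each arm. The patients who would drop out are the earliest failures, so the error can only flatter the estimates.

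**Working it through.** The documents state no PFS rate, PFS event count or early-death rate in visible text, so there is no plan figure to reproduce. The check is the algebra of the rule, followed by its size under stated assumptions.

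**Step 1: effect of day-0 censoring.** Let e be the fraction of an arm that dies before any post-baseline scan, and S the true 6-month PFS. With no other events or censoring before the first scan,

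S = (1 − e) × P(event-free at 6 months, given alive past the first-scan period).

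A patient censored at day 0 is never in the risk set at an event time, so the factor (1 − e) disappears and the reported rate is S/(1 − e).

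**Step 2: size, with S = 35% assumed.**

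| e (assumed) | Deaths before any scan, of 80 / of 40 | Reported rate | Excess |
|---|---|---|---|
| 2.5% | 2 / 1 | 0.35/0.975 = 35.9% | +0.9 points |
| 5% | 4 / 2 | 0.35/0.95 = 36.8% | +1.8 points |
| 7.5% | 6 / 3 | 0.35/0.925 = 37.8% | +2.8 points |
| 8% | about 6 / about 3 | 0.35/0.92 = 38.0% | +3.0 points |

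For e of 2.5% to 7.5% and true rates of 20% to 45%, the excess runs from 0.20/0.975 − 0.20 = 0.5 points to 0.45/0.925 − 0.45 = 3.6 points.

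**Step 3: is that range of e plausible?** The documents give no figure for this trial. As an assumption, borrow the first-line pembrolizumab monotherapy median OS values in Section 1.2.2 (12.3 and 14.9 months) and a constant death hazard. Week 6 is 42/30.44 = 1.38 months.

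- Median 12.3 months: 1 − 2^(−1.38/12.3) = 7.5% dead by Week 6.
- Median 14.9 months: 1 − 2^(−1.38/14.9) = 6.2%.

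Across the Week 5 to 7 window the range is about 5% to 9%. A constant hazard probably overstates e here, for the eligibility reasons given under the objection.

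**Step 4: cross-check by simulation.** 400,000 patients per scenario, scans on the protocol schedule, and a death hazard before progression of 0.6 times the constant OS hazard. Accrual was uniform over 43 − 24 = 19 months (Section 3.2), with cutoff 6 or 24 months after the last patient. Assumed median PFS was 2.6 months (Section 1.7.1), 5.6 months (Section 1.2.1) and 4.0 months in between. The simulated e was 4.1% to 5.4%.

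| Assumed median PFS | 6-month PFS, deaths counted | With day-0 rule |
|---|---|---|
| 2.6 months | 22.5–22.7% | 23.7–23.8% |
| 4.0 months | 37.7–37.9% | 39.4–39.7% |
| 5.6 months | 49.6–49.8% | 51.9–52.2% |

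The excess is +1.1 to +2.6 points and agrees with the formula: for example, 0.496/(1 − 0.050) = 52.2%.

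**Step 5: scale.** Ignoring censoring, the 95% half-width at a 35% rate is 1.96 × √(0.35 × 0.65/80) = 10 points for 80 patients and 1.96 × √(0.35 × 0.65/40) = 15 points for 40.

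**The case against.** The best defence is that the definition governs and censoring applies only to patients without an event. On that reading the second sentence merely supplies a fallback date when there is no last tumor assessment to use. This is a natural reading and may be what was meant. It does not remove the problem, because the sentence covers everyone without a scan and nothing visible limits it to event-free patients.

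The defence is also right that e may be small. Section 4.1.1 requires ECOG 0 or 1 and a life expectancy of at least 12 weeks. Section 4.1.2 excludes rapidly progressing disease. Section 4.5.6 calls for scans whenever progression is suspected, so some patients who die before Week 6 will have been scanned. The bias is also well inside the confidence interval, though it is systematic and avoidable.

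Two stronger readings are tempting, and the documents do not support them.

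- *That living progressors would be censored because of the 'or'.* Taken literally, only patients who both progressed and died would be events. In the same simulation, with the day-0 rule also applied, that raises 6-month PFS by 11 to 32 points. But it would void the definition given just before it, and the 'and' in Section 6.4.2.1 shows the likely intent. It is almost certainly a drafting slip, and those figures should not be used to judge severity.
- *That the comparison between arms is biased.* With 8% early deaths in one arm and 3% in the other, a shared true rate of 35% would show 0.35/0.92 − 0.35/0.97 = 1.9 points of false difference. That split has no source in the documents, and Section 6.4.2.2 gives per-arm estimates only, with no visible test, hazard ratio or difference.

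**Conclusion.** The point holds in a limited form. The day-0 sentence contradicts the protocol's own PFS definition for patients who die before a scan. If programmed as written, it overstates the 6-month PFS rate by about 1 to 3 points, assuming a true rate of 35% and 2.5% to 8% of an arm dying unscanned. The lower end is more likely given the eligibility criteria. The median moves in the same direction, but in steps, because progressions are recorded on scan dates.

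Whether any bias arises depends on how the sentence is programmed, which the documents do not settle. The effect is confined to secondary, descriptive, per-arm PFS estimates. The primary confirmed response rate is unaffected, and early deaths remain events in OS. It is worth correcting because a stated rule is wrong as written, not because the trial's main conclusion depends on it.

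**What to change.** Replace the two censoring sentences in Section 6.4.2.2 with text to this effect:

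*A patient who has neither progressed nor died by the cutoff is censored at the latest tumor assessment, or on the randomization date if none was done after baseline. A death with no earlier documented progression is a PFS event on the date of death, with or without a post-baseline assessment.*

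This corrects the 'or' at the same time. If programs already exist, check which rule they apply. Reporting the number of deaths without a post-baseline assessment in each arm would let a reader see e directly.

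The cost is two sentences, with no change to data collection or patient management. The one downside for the sponsor is that PFS may look slightly less favourable.

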6.4.2.3 Overall Survival, Including Overall Survival Rate at 6 Months and 12 Months

OS is defined as the time between the date of randomization and death from any cause. Data for patients who are not reported as having died by the data cutoff date will be censored at the date when they were last known to be alive. Data for patients who do not have post-baseline information will be censored at the date of randomization.

OS and OS rate at 6 months and 12 months will be analyzed using the same methods as described in Section [6.4.2.2](#).

6.4.2.4 Patient-Reported Outcomes

TTCD for physical functioning using the PROMIS® Item Bank v2.0–Physical Functioning–Short Form 10b is defined as the time from the date of randomization until the first confirmed clinically meaningful deterioration. Confirmed clinically meaningful deterioration in physical function is defined as a clinically meaningful decrease from baseline that must be held for at least two consecutive assessments, or an initial clinically meaningful decrease from baseline followed by death. A T-score change >4 points is considered to be clinically meaningful for the physical functioning subscale score (Yost et al. 2011).

TTCD will be assessed in all randomized patients who received at least one dose of study treatment. Patients will be grouped based on actual treatment received. Patients who have not experienced a confirmed clinically meaningful deterioration at the clinical cutoff date will be censored at the last time when they completed an assessment. If no baseline or post-baseline assessment is performed, patients will be censored at the randomization date. TTCD [REDACTED] will be analyzed using the same methods as for PFS.

[REDACTED]

[REDACTED]

[REDACTED]

6.5 SAFETY ANALYSES

The safety analysis population will consist of all randomized patients who received at least one dose of atezolizumab or tiragolumab/placebo.

Safety analyses will be performed by treatment arm and will be based on actual treatment received. Specifically, a patient will be included in the atezolizumab plus tiragolumab arm in the safety analyses if the patient receives any amount of tiragolumab, regardless of the initial treatment assignment at randomization.

Drug exposure will be summarized, including duration, dosage, and dose intensity. Verbatim description of adverse events will be mapped to the MedDRA thesaurus terms and graded according the NCI CTCAE v5.0, and severity for CRS will also be graded by the investigator according to the ASTCT Consensus Grading Scale. All adverse events will be summarized by treatment arm and NCI CTCAE grade. CRS will also be summarized by treatment arm and ASTCT consensus grade. In addition, serious adverse events, immune-mediated adverse events, and adverse events leading to study treatment discontinuation or interruption will be summarized accordingly. Multiple occurrence of the same event will be counted once at the maximum severity.

All deaths and causes of deaths will be summarized by treatment arm.

Laboratory data with values outside of the normal ranges will be identified. Additionally, selected laboratory data, including ADA results, will be summarized.

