As of the primary clinical cutoff date of 30 June 2019, the investigator-assessed PFS in all randomized patients who received at least one dose of study treatment. Patients were grouped according to treatment received and investigator-assessed PFS was improved in the tiragolumab plus atezolizumab group compared with the placebo plus atezolizumab group (stratified HR=0.57; 95% CI: 0.37 to 0.90; median PFS 5.4 vs. 3.6 months, respectively). In the subgroup of patients with TPS $\geq 50\%$, investigator-assessed PFS was improved in the tiragolumab plus atezolizumab group compared with the placebo plus atezolizumab group (unstratified HR=0.33; 95% CI: 0.15 to 0.72; median PFS: not estimable [NE] vs. 3.9 months, respectively). With an additional 6 months of follow-up (clinical cutoff date of 2 December 2019), the PFS benefit was maintained in all randomized patients who received at least one dose of study treatment. Patients were grouped according to treatment received (stratified HR=0.58; 95% CI: 0.38 to 0.89; median PFS 5.5 vs. 3.88 months) and the TPS $\geq 50\%$ population (unstratified HR=0.30; 95% CI: 0.15 to 0.61; median PFS: NE vs. 4.11 months) (Rodriguez-Abreu et al. 2020). DOR and OS data were not yet mature as of the clinical cutoff date.

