5.3.1 Adverse Event Reporting Period

Investigators will seek information on adverse events at each patient contact. All adverse events, whether reported by the patient or noted by study personnel, will be recorded in the patient's medical record and on the Adverse Event eCRF.

After informed consent has been obtained but prior to initiation of study treatment, only serious adverse events caused by a protocol-mandated intervention (e.g., invasive procedures such as biopsies, discontinuation of medications) should be reported (see Section 5.4.2 for instructions for reporting serious adverse events).

After initiation of study treatment, all adverse events will be reported until [REDACTED] days after the final dose of study treatment [REDACTED], and serious adverse events will continue to be reported until [REDACTED] days after the final dose of study treatment [REDACTED]. In addition, adverse events of special interest will continue to be reported until [REDACTED] days after the final dose of study [REDACTED].

Instructions for reporting adverse events that occur after the adverse event reporting period are provided in Section 5.6.

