5.6 ADVERSE EVENTS THAT OCCUR AFTER THE ADVERSE EVENT REPORTING PERIOD

After the end of the reporting period for serious adverse events and adverse events of special interest (reporting periods defined in Section 5.3.1) all deaths, regardless of cause, should be reported through use of the Long-Term Survival Follow-Up eCRF.

In addition, if the investigator becomes aware of a serious adverse event that is believed to be related to prior exposure to study treatment, the event should be reported through use of the Adverse Event eCRF. However, if the EDC system is not available, the investigator should report these events directly to the Sponsor or its designee, either by faxing or by scanning and emailing the paper Clinical Trial Serious Adverse Event/ Special Situation Reporting Form using the fax number or email address provided to investigators.

5.7 EXPEDITED REPORTING TO HEALTH AUTHORITIES, INVESTIGATORS, INSTITUTIONAL REVIEW BOARDS, AND ETHICS COMMITTEES

The Sponsor will promptly evaluate all serious adverse events and adverse events of special interest against cumulative product experience to identify and expeditiously communicate possible new safety findings to investigators, IRBs, ECs, and applicable health authorities based on applicable legislation.

The Sponsor has a legal responsibility to notify regulatory authorities about the safety of a study treatment under clinical investigation. The Sponsor will comply with regulatory requirements for expedited safety reporting to regulatory authority (which includes the use of applicable systems, such as EudraVigilance), IRBs, ECs, and investigators.

To determine reporting requirements for single adverse event cases, the Sponsor will assess the expectedness of these events through use of the reference safety information in the documents listed below:

Drug	Document
Tiragolumab	Tiragolumab Investigator's Brochure
Atezolizumab	Atezolizumab Investigator's Brochure

The Sponsor will compare the severity of each event and the cumulative event frequency reported for the study with the severity and frequency reported in the applicable reference document.

Reporting requirements will also be based on the investigator's assessment of causality and seriousness, with allowance for upgrading by the Sponsor as needed.

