An IMC will monitor the incidence of the above-listed anticipated events during the study. An aggregate report of any clinically relevant imbalances that do not favor the test product will be submitted to health authorities.

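### Section 6.5 plans only crude adverse event incidence by arm, although collection ends relative to the last dose; if treatment durations differ, incidence is inflated in the longer-treated arm

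*Combined protocol and SAP*

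**What the plan says.** **Collection.** Section 5.3.1 ties recording to the last dose: "After initiation of study treatment, all adverse events will be reported until [REDACTED] days after the final dose of study treatment". Two further limits follow: "serious adverse events will continue to be reported until [REDACTED] days after the final dose of study treatment", and "adverse events of special interest will continue to be reported until [REDACTED] days after the final dose of study" treatment. All three lengths are redacted, as are the clauses after them. Once these periods close, Section 5.6 keeps deaths, and adds a serious event to the Adverse Event eCRF "if the investigator becomes aware of a serious adverse event that is believed to be related to prior exposure to study treatment".

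**Treatment duration.** Section 3.3 runs treatment to progression. Sections 3.1.1 and 4.6.1 allow continuation beyond radiographic progression under conditions, until clinical benefit is lost. Toxicity and other reasons can also end treatment.

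**Analysis.** The safety endpoint in Section 2.2 is incidence and severity. Section 6.5 states: "All adverse events will be summarized by treatment arm and NCI CTCAE grade". Serious events, immune-mediated events and events leading to discontinuation or interruption are summarized in the same way, and a repeated event counts once at its worst grade. Duration of exposure, dosage and dose intensity are also summarized. The section gives no onset window for the tables, no rate per unit of time at risk, and no time-to-first-event or fixed-period summary.

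**The concern.** A patient still on treatment remains under full adverse event collection. A patient who has stopped leaves it a set number of days later. Because progression is a main reason for stopping, an arm that delays progression is watched for longer. A simple proportion with at least one event then mixes two things: how often events occur per unit of time, and how long patients were observed.

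The benefit-risk argument in Section 1.8.2 is that adding tiragolumab may increase efficacy without adding toxicity. If the first part is true, exposure will probably differ between arms, and crude incidence cannot then cleanly address the second part. The distortion can work either way: an excess may reflect only longer observation, and similar crude incidence under longer exposure may hide a lower rate. The plan uses Kaplan-Meier methods with censoring for PFS, OS and time to confirmed deterioration (Sections 6.4.2.2 to 6.4.2.4). The safety tables have no counterpart.

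**Working it through.** The plan gives no expected event rate, exposure or person-time, so there is no figure of its own to reproduce. What follows is an illustration under stated assumptions.

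**Inputs from the documents**
- Allocation (Section 6.1): 120 patients at 2:1, so 120 × 2/3 = 80 and 120 × 1/3 = 40.
- Proxy for time on treatment (Section 1.6.2.3, GO40290, same two regimens in lung cancer): "median PFS 5.4 vs. 3.6 months, respectively"; at the later cutoff, 5.5 vs 3.88 months.
- Control incidences for calibration (Section 1.6.2.2, GO40290): Grade 3-5 44.1% (30/68) and serious 35.3% (24/68).

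**Assumptions**
- Time on treatment is exponential with the proxy median m.
- The event hazard λ is constant and equal in both arms, so there is no true difference.
- The all-event window W after the last dose is 0, 30 or 90 days, because the real length is redacted.
- A control incidence of 10% is added to represent a less common event.

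**Formula.** With μ = ln 2 / m and W in months:

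crude incidence = 1 − exp(−λW) × μ / (μ + λ)

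λ is solved to give the chosen control incidence, then applied unchanged to the longer-treated arm.

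**One case in full:** control 44.1%, W = 30 days = 0.986 months, λ = 0.1150 per month.
- Control: μ = ln 2 / 3.6 = 0.1925. Incidence = 1 − 0.8928 × 0.1925 / 0.3075 = 0.441.
- Longer-treated arm: μ = ln 2 / 5.4 = 0.1284. Incidence = 1 − 0.8928 × 0.1284 / 0.2434 = 0.529.
- The artefact is 8.8 points. The rate per time at risk is 11.5 first events per 100 patient-months in both arms.

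**Artefact in percentage points**

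| Proxy medians (months) | Control incidence | W = 0 | W = 30 days | W = 90 days |
|---|---|---|---|---|
| 5.4 vs 3.6 | 10% | 4.3 | 3.6 | 2.8 |
| 5.4 vs 3.6 | 35.3% | 9.7 | 8.4 | 6.7 |
| 5.4 vs 3.6 | 44.1% | 10.1 | 8.8 | 7.1 |
| 5.5 vs 3.88 | 10% | 3.6 | 3.1 | 2.4 |
| 5.5 vs 3.88 | 35.3% | 8.3 | 7.2 | 5.8 |
| 5.5 vs 3.88 | 44.1% | 8.7 | 7.6 | 6.2 |

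**Limits of the effect**
- Equal durations (3.6 vs 3.6 months): 0 in every case.
- Hazard confined to the first 0.7 month, control 10%: 10.2% in the longer-treated arm at W = 0, and 10.0% at 30 and 90 days.
- Control incidence 95.6% (any adverse event in GO40290): 1.1 to 1.4 points.

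**Scale.** The standard error of a difference at 44.1% with 80 and 40 patients is √(0.441 × 0.559 × (1/80 + 1/40)) = 9.6 points. The artefact is at most about one standard error, but it is a bias and does not shrink with more patients.

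**The case against.** The strongest reply is that crude by-arm tables match the stated endpoint in a descriptive Phase II trial, and that exposure duration is tabulated, so a reader can see any imbalance. The first part stands. The second gives context but corrects no incidence figure.

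The size also rests on proxies. PFS in another tumour type is not time on treatment: treatment may continue past progression and may stop for toxicity. The windows are assumed. This stands, and is why a range is given.

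Several stronger readings are tempting, and the documents do not support them:
- *The longer-treated arm must show more events.* The effect needs unequal durations and events that keep accruing. GO40290 had longer PFS with the combination, yet crude incidence was slightly lower for Grade 3-5 (41.8% vs 44.1%) and serious events (34.3% vs 35.3%). Immune-mediated events were more frequent (65.7% vs 47.1%), a difference attributed mainly to rash and infusion reactions; any part arising in the first cycle would owe little to duration.
- *Collection runs through successively shorter windows.* The lengths are redacted. What narrows after the all-event window is the scope of events, since "and serious adverse events will continue to be reported until" a further limit.
- *Section 6.5 formally compares the arms.* It summarizes by arm and plans no test or contrast.
- *Late serious-only reports are pooled in and shift the grades upward.* Section 6.5 is silent on onset windows, so pooling is an inference, and the shift cannot be sized.
- *The Section 5.7 report depends on these tables.* That section says "An aggregate report of any clinically relevant imbalances that do not favor the test product will be submitted to health authorities", but concerns a list of anticipated events not visible in the public text, calls for clinical judgement, and does not name the Section 6.5 tables as its source.

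**Conclusion.** The point holds as a conditional reporting gap. Observation time for adverse events follows time on treatment, and Section 6.5 specifies only crude summaries. If durations differ, those summaries overstate the longer-treated arm for events that keep accruing, even at equal hazards.

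The illustrated size is about 6 to 10 points at a control incidence of 35 to 44% across both pairs of medians, and 3 to 4 points at 10% with medians of 5.4 and 3.6 months. It is negligible for first-cycle events and zero with equal durations. These figures assume exponential durations, constant equal hazards, GO40290 PFS as a stand-in for exposure, and a 0- to 90-day window. They show what could happen; they do not predict this trial's result. No stated figure in the plan is wrong, and the gap is worth closing because the remedy is cheap.

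**What to change.** In Section 6.5:

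1. Keep the crude by-arm, by-grade tables. State that they cover events with onset from first dose to the end of the all-adverse-event window in Section 5.3.1, and tabulate later serious, special-interest and post-period events separately.
2. Beside them, give exposure-adjusted incidence: patients with a first event per 100 patient-years at risk, counting time from first dose to the first event or the end of that window.
3. Add cumulative incidence over a common early period, for example first dose to Week 12, stating how death and an earlier end of collection are handled.
4. Do this for all, Grade 3-5, serious and immune-mediated events.

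The cost is a paragraph of analysis text and a few tables; event dates and dosing dates are already recorded. The drawback is that a rate per patient-year is easy to interpret only when the hazard is roughly constant. The fixed-period incidence does not need that assumption, which is why both are shown.
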